7.1.1.4 Investigational Product Accountability

Study site staff will maintain a record of the IP received, dispensed, administered, and destroyed. All records will be maintained with controlled access. An unblinded study monitor will perform IP accountability and compliance monitoring during the study. The Investigator will administer the IP only to subjects included in this study and according to the procedures established in this study protocol. Each administration of study product will be documented and transferred to the eCRF.

7.1.1.5 VIB4920 Handling and Disposal

The Investigator or designee must return any unused vials of VIB4920 to Viela Bio or designee regardless of whether the study was completed or terminated prematurely. At the time of return, the Investigator must verify that unused or partially used IPs have been returned and that no IPs remain at the site. As an alternative to returning unused IP at the end of the study, the Investigator may destroy unused IP on site with agreement from Viela Bio.

7.1.2 Placebo

7.1.2.1 Formulation, Storage, Preparation, and Handling

Placebo will be 0.9% (w/v) saline provided by the site as 250 mL prefilled IV bags.

7.1.2.2 Dosing and Administration

For each dose of placebo, one 250 mL IV bag containing 0.9% (w/v) saline and one IV infusion pump is required for administration.

7.2 Treatment Assignment and Bias Minimization

7.2.1 Treatment Allocation

Subjects will be randomized 1:1:1:1:1 by IXRS to Cohorts 1 to 5 using a parallel-cohort design.

IP (VIB4920 or placebo) must be administered the same day the IP is assigned. If there is a delay in the administration of IP such that it will not be administered within the specified timeframe, the study monitor must be notified immediately.

7.2.2 Randomization Strategy and Procedure

An IXRS will be used for randomization to a treatment group and assignment of IP kit numbers. A subject is considered randomized into the study when the Investigator notifies the IXRS that the subject meets eligibility criteria and the IXRS provides the assignment of treatment group.

Additional details are provided in the IXRS Manual.

7.2.3 Extent and Maintenance of Blinding

This is a double-blind study in which VIB4920 and the saline placebo are not identical in appearance. For maintaining the blinding of the subjects, Investigators, site staff, Sponsor, CRO and staff, a local unblinded pharmacy staff member will be nominated by each site and will have the responsibility of allocating, dispensing, and preparing the IP, and covering the IV bags with an opaque bag to maintain the blind.

In addition, a separate unblinded monitor will be used for the oversight of IP management. If treatment allocation for a subject becomes known to the Investigator or other study staff involved in the management of study subjects, the Sponsor must be notified immediately.

7.2.4 Unblinding Procedures

7.2.4.1 Unblinding in the Event of a Medical Emergency

In the event of a medical emergency, the Investigator may unblind an individual subject's IP allocation. Instructions for unblinding an individual subject's IP allocation are contained in the IXRS manual. In general, unblinding should only occur if management of the medical emergency would be different based on the subject having received IP. In the majority of cases, the management of a medical emergency would be the same whether or not IP was received by the subject. If this was the case, the IP allocation should not be unblinded.

7.2.4.2 Unblinding for the Primary (Interim) Analysis

The primary efficacy analysis will be conducted after all subjects have completed the Day 113 visit (Visit 7) or discontinued early from the study. As the primary analysis will be an interim analysis, a small prespecified number of Sponsor staff who are not directly involved in the conduct of the study will be unblinded for decision-making purposes. Study site personnel, subjects, and CRO and Sponsor personnel directly associated with the conduct of the study will remain blinded to the treatment assignment for individual subjects and the results of the primary (interim) analysis until the completion of the study.

7.3 Assessment and Verification of Compliance

Site staff will administer all IPs IV at the study center. The dose and date of administration of IP must be recorded in the subject eCRF. Treatment compliance will be assessed based on this information.

7.4 Concomitant Medications and Treatments

Although subjects are asked to remain on their stable background medications until the Day 85 visit, subjects should receive all medications, including treatments for RA, that are considered by their physician to be necessary for their health.

The Sponsor recommends that Investigators ensure that all patients are up to date with required vaccinations prior to entry into the study.

7.4.1 Prohibited Medications

If a subject receives any of the listed prohibited medications after the screening visit and prior to Day 85, the Investigator must notify the Sponsor/designee Medical Monitor immediately. These changes in medications must be clearly recorded, with the reason for the change, in the eCRF. The prohibited medications are:

- Rescue medication prior to Day 85 (defined in Section [7.4.2](#))
- Investigational agents
- Live vaccines or live therapeutic infectious agents
- Plasmapheresis or plasma exchange

7.4.2 Rescue Therapy

Rescue therapy is any new or intensified immunosuppressive, conventional, or bDMARD treatment for RA, including:

- Initiation of or increase in dose of any cDMARD
- Initiation of a bDMARD therapy or JAK inhibitor therapy
- Increase in baseline corticosteroid dose
- Intraarticular steroid injection > 40 mg methylprednisolone (or its equivalent) OR more than one intraarticular steroid injection of any dose. One intraarticular steroid injection ≤ 40 mg methylprednisolone in one joint is permitted and not considered rescue therapy.

If a subject receives rescue therapy prior to the final dose of IP, IP will be discontinued (Section [6.5.1](#)).

Subjects administered rescue therapy do not need to be followed until Day 309 but can complete the study at or after Day 113. Subjects must also complete a 3-month safety follow-up period after the final dose of IP and must return for at least one visit after initiating rescue therapy to complete remaining assessments ([Table 8](#)).

Table 8 Alternate Study Completion Schedules Following Rescue Therapy

Last Dose Prior to Rescue Therapy	Last Study Visit
≤ Dose 3 (Day 29 ± 3d)	Day 113 OR + 1 visit post-initiation of rescue therapy, whichever is later
≥ Dose 4 (Day 57 ± 3d)	Day 141 OR + 1 visit post-initiation of rescue therapy, whichever is later

Note: All actions include the required Day 113 visit, 3 months of follow-up, and one visit post-initiation of rescue therapy.

8 SAFETY ASSESSMENTS

An independent SDMC will perform evaluations of safety data at specified regular intervals throughout the study and make recommendations to the Sponsor regarding further conduct of the study. See Section [11.1](#) for details on SDMC activities.

8.1 Definitions

- **Adverse event** – An AE is any untoward medical occurrence associated with the use of an intervention in humans whether or not it is considered intervention-related.
- **Serious adverse event** – A SAE is considered “serious” if, in the view of either the Investigator or Sponsor, it results in any of the following outcomes:
 - Death
 - A life-threatening AE. (An event is considered “life-threatening” if, in the view of either the Investigator or Sponsor, its occurrence places the patient or subject at immediate risk of death. It does not include an AE or suspected adverse reaction (SAR) that, had it occurred in a more severe form, might have caused death.)
 - Inpatient hospitalization or prolongation of existing hospitalization
 - A persistent or significant incapacity or substantial disruption of the ability to conduct normal life functions
 - A congenital anomaly/birth defect
 - Important medical events that may not result in death, be life-threatening, or require hospitalization may be considered serious when, based upon appropriate medical judgment, they may jeopardize the patient or subject and may require medical or surgical intervention to prevent one of the outcomes listed in this definition. Examples of such medical events include allergic bronchospasm requiring intensive treatment in an emergency room or at home, blood dyscrasias or convulsions that do not result in inpatient hospitalization, or the development of drug dependency or drug abuse.
- **Causality or relatedness:** The Investigator is required to provide an assessment of the relationship of AEs and SAEs to the IP. An event will be considered “not related” to use of IP if any of the following tests are met:

- An unreasonable temporal relationship between administration of the IP and the onset of the event (eg, the event occurred either before, or too long after, administration of the IP for it to be considered IP-related)
- A causal relationship between the IP and the event is biologically implausible (eg, death as a passenger in an automobile accident)
- A clearly more likely alternative explanation for the event is present (eg, typical adverse reaction to a concomitant drug and/or typical disease-related event)

Individual AE/SAE reports will be considered “related” to use of the IP if the “not related” criteria are not met.

“Related” implies that the event is considered to be “associated with the use of the drug” meaning that there is “a reasonable possibility” that the event may have been caused by the IP (ie, there are facts, evidence, or arguments to suggest possible causation).

- **Adverse reaction** – An adverse reaction is any AE caused by a drug.
- **Suspected adverse reaction** – A SAR is any AE for which there is a reasonable possibility that the drug caused the AE. For the purposes of safety reporting to regulatory agencies, “reasonable possibility” means there is evidence to suggest a causal relationship between the drug and the AE. SAR implies a lesser degree of certainty about causality than an adverse reaction.
- **Unexpected** – An event is considered unexpected if it is not listed in the IB, is not listed at the specificity or severity that has been observed, or, if an IB is not required or available, is not consistent with the risk information described in the General Investigational Plan or elsewhere. Unexpected also refers to events that are mentioned in the IB as occurring with a class of drugs or as anticipated from the pharmacological properties of the drug but are not specifically mentioned as occurring with the particular IP.
- **Severity or intensity:** Severity will be assessed according to the following scale:
 - Grade 1: An event of mild intensity that is usually transient and may require only minimal treatment or therapeutic intervention. The event does not generally interfere with usual activities of daily living.
 - Grade 2: An event of moderate intensity that is usually alleviated with additional, specific therapeutic intervention. The event interferes with usual activities of daily living, causing discomfort but poses no significant or permanent risk of harm to the subject.
 - Grade 3: A severe event that requires intensive therapeutic intervention. The event interrupts usual activities of daily living, or significantly affects the clinical status of the subject.
 - Grade 4: An event, and/or its immediate sequelae, that is associated with an imminent risk of death or with physical or mental disabilities that affect or limit the ability of the subject to perform activities of daily living (eating, ambulation, toileting, etc).
 - Grade 5: Death (loss of life) as a result of an event.

8.2 Documenting Adverse Events

AEs spontaneously reported by the subject and/or in response to an open question from the study personnel or revealed by observation will be recorded during the study at the investigational site. For each AE, the Investigator will evaluate and report the onset (date and time), resolution (date and time), severity, causality, action taken, serious outcome (if applicable), and whether or not it caused the subject to discontinue the study. The AE term should be reported in standard medical terminology when possible.

8.3 Reporting Adverse Events

All AEs (related and unrelated) will be recorded from written ICF signature up to the end of the study, whether or not they are related to the study. Any SAEs considered related to the IP and discovered by the Investigator at any time after the study should be reported.

All SAEs must be reported within 24 hours by submitting a SAE Report Form by email to:

[REDACTED]
[REDACTED]

Alternatively, the SAE Report Form can be submitted by fax to:

[REDACTED]
[REDACTED]

Additional follow-up information, if required or available, should all be reported within one business day of receipt, should be completed on a follow-up SAE form, placed with the original SAE information and kept with the appropriate section of the eCRF and/or study file.

The designated Sponsor representative (ICON) will work with the Investigator to ensure that all the necessary information is provided within one calendar day of initial receipt for fatal and life-threatening events and within 5 calendar days of initial receipt for all other SAEs.

Viela Bio or designee is responsible for notifying the relevant regulatory authorities of certain events. It is the PI's responsibility to notify the IRB or IEC of all SAEs that occur at his or her site. Investigators will also be notified of all unexpected, serious, drug-related events (7/15 Day Safety Reports) that occur during the clinical trial. Each site is responsible for notifying its IRB or IEC of these additional SAEs.

8.4 Adverse Events of Special Interest

An AESI is an AE of scientific and medical interest specific to understanding of the IP and may require close monitoring and collection of additional information by the Investigator. An AESI may be serious or nonserious. The rapid reporting of AESIs allows ongoing surveillance of these events in order to characterize and understand them in association with the use of this IP.

The following AESIs will be particularly monitored in this study and should be reported to ICON Patient Safety within 24 hours of awareness as in Section 8.3.

- Thrombotic and embolic events
- Anaphylaxis and clinically significant (Grade 3 or higher) hypersensitivity reactions (see [Appendix 1](#) for guidance on diagnosis of anaphylaxis reactions)
- Severe infusion-related reactions (CTCAE Grade 3 or higher; [Table 9](#))

- Immune complex disease
- Severe (Grade 3 or higher) and/or opportunistic infections
- Hepatic function abnormality meeting the definition of Hy's Law (see [Appendix 2](#))
- Malignant neoplasm

Table 9 CTCAE Grading of Infusion-related Reactions

Grade 1	Mild transient reaction; infusion interruption not indicated; intervention not indicated
Grade 2	Therapy or infusion interruption indicated but responds promptly to symptomatic treatment (eg, antihistamines, NSAIDs, narcotics, IV fluids); prophylactic medications indicated for ≤ 24 hrs
Grade 3	Prolonged (eg, not rapidly responsive to symptomatic medication and/or brief interruption of infusion); recurrence of symptoms following initial improvement; hospitalization indicated for clinical sequelae
Grade 4	Life-threatening consequences; urgent intervention indicated
Grade 5	Death

CTCAE = Common Terminology Criteria for Adverse Events; IV = intravenous; NSAID = nonsteroidal anti-inflammatory drug.

Note: These CTCAE grades are specific to infusion-related reactions.

Source: Common Terminology Criteria for Adverse Events v5.

8.5 Clinical Laboratory Findings

Blood, urine and respiratory (swab or saliva) samples will be collected for laboratory safety tests as specified in the Schedule of Assessments shown in [Table 2](#) (screening) and [Table 3](#) (treatment period). Laboratory testing is described below. For further details regarding laboratory assessments, see the Study Laboratory Manual.

8.5.1 Hematology

The hematology panel will include a complete blood count, with white blood cell count (WBC) and differential (basophils, eosinophils, lymphocytes, monocytes, and neutrophils), hemoglobin, hematocrit, and platelet count.

8.5.2 Serum Chemistry

Serum chemistry assessments will include:

- Albumin
- Alkaline phosphatase (ALP)
- ALT
- AST
- Bicarbonate
- Blood urea nitrogen
- CRP
- Calcium
- Chloride
- Cholesterol
- Creatinine
- HbA1C
- Immunoglobulins: Total, IgA, IgG, and IgM
- Magnesium
- Phosphorus
- Potassium
- Sodium
- TBL (if > 1.5 ULN, indirect and direct bilirubin will be measured)
- Total protein
- Triglycerides (fasting not required unless abnormal at baseline, in which case an 8-hour fast is required)

- Gamma-glutamyl transferase
- Uric acid
- Glucose (random)

Tests for AST, ALT, ALP, and TBL must be conducted concurrently and assessed concurrently.

8.5.3 Coagulation Parameters

Coagulation parameters will include prothrombin time and PTT.

8.5.4 Urinalysis

Urinalysis will evaluate color, appearance, and specific gravity. Dipstick analysis will include pH, protein, glucose, blood, ketones, and bilirubin. Samples with abnormal dipstick will have microscopy performed. Microscopy will include WBC/HPF (high power field) and red blood cell count/HPF.

8.5.5 Testing for SARS-CoV-2

The investigator must ensure that the subject has a documented negative SARS-CoV-2 viral test within two weeks prior to randomization. Testing for antibodies to SARS-CoV-2 will not meet the testing requirement.

8.6 Vital Signs, Body Weight, and Physical Examinations

Vital signs, including systolic and diastolic blood pressure (mmHg), pulse rate (beats/min), respiratory rate (breaths/min), body temperature (°C), and body weight (kg), will be measured using clinically acceptable methods and devices as defined in the schedule of assessments in [Table 2](#) (screening), [Table 3](#) (treatment period), and the IP Administration Manual.

Depending on the visit, physical examinations will be either a full examination (with the exception of rectal and pelvic examinations) or a symptom-driven examination.

8.7 Electrocardiogram

A 12-lead ECG will be performed according to the schedule of assessments in [Table 2](#) (screening) and [Table 3](#) (treatment period). All ECG recordings will be made with the subject in a supine position, having rested in this position for at least 5 minutes before the start of the ECG.

Each ECG will include ventricular heart rate and intervals (PR, QRS, QT, QTc). The Investigator will be responsible for providing an interpretation of the ECG. Clinically significant abnormalities will be recorded as AEs.

8.8 Pregnancy

Serum β-hCG pregnancy test(s) will be completed for all females during the screening period and urine pregnancy tests will be completed in females of childbearing potential at all subsequent study visits ([Table 3](#)). At Visits 2 through 5 (dosing visits), pregnancy testing must be completed prior to administration of IP. Urine pregnancy tests will be performed at the site.

8.9 Overdose or Misuse

Any instance of overdose (suspected or confirmed and irrespective of whether or not it involved VIB4920) must be communicated to Viela Bio or a specified designee within 24 hours and be fully documented as a SAE. Details of any signs or symptoms and their management should be recorded, including details of any antidote(s) administered.

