3.6 Safety Analysis

3.6.1 Adverse Events

In general, if an AE onset is on or after the first dose of IP administration, the AE will be considered as a TEAE. Otherwise, the AE will be considered as a non-treatment emergent AE.

An overall summary table will be showing the number and percentage of subjects with at least 1 event in any of the following categories: TEAE, TESAE, TEAE with outcome of death, TEAE leading to discontinuation of IP, grade 3 or higher TEAE, serious and/or grade 3 or higher TEAE, IP related TEAE, IP related TESAE.

AEs will be coded using the most recent version of MedDRA. All TEAEs will be summarized overall and by MedDRA SOC and PT, by severity and by relationship to IP. Specific AEs will be counted once for each subject for calculating rates, but all events will be presented in subject listings. In addition, if the same AE occurs multiple times within a particular subject, the highest severity and level of causality will be reported.

The TEAEs, TESAEs, TEAEs resulting in death, TEAEs leading to discontinuation of IP, Grade 3 or higher TEAEs, IP related TEAEs, and IP related TESAEs will be summarized by SOC and PT. TESAEs will be summarized by SAE criteria as well. In addition, a summary of TEAEs sorted by frequency will be presented by PT.

An AESI is one of scientific and medical interest specific to understanding of the IP. AESIs for this protocol include:

- Thrombotic and embolic events
- Anaphylaxis and clinically significant (Grade 3 or higher) hypersensitivity reactions
- Severe Infusion-related reactions (common terminology criteria for adverse event (CTCAE) Grade 3 or higher)
- Immune complex disease
- Severe (Grade 3 or higher) and/or opportunistic infections
- Hepatic function abnormality (meeting the definition of Hy's Law)
- Malignant neoplasm

TEAESIs will be summarized by SOC and PT.

Listings will be provided for all TEAEs and non-treatment emergent AEs.

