3.6.3 Other Safety Evaluations

3.6.3.1 Overdose

The incidence of TEAE associated with overdose will be summarized by MedDRA SOC and PT if applicable.

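### Protocol 8.9 has every overdose recorded as an SAE with no seriousness test, so an overdose that meets no 8.1 criterion could be counted as a TESAE

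*Protocol*

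**What the plan says.** Protocol 8.9 (Overdose or Misuse) covers overdose in the widest terms, "suspected or confirmed and irrespective of whether or not it involved VIB4920", and requires each instance to be communicated "within 24 hours and be fully documented as a SAE". It continues: "Details of any signs or symptoms and their management should be recorded". Symptoms are therefore details to capture and do not trigger the rule.

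Protocol 8.1 defines seriousness by consequence. An event is serious if, "in the view of either the Investigator or Sponsor, it results in any of the following outcomes". The list includes a route for important medical events, which rests on medical judgment about the individual case. Overdose is neither a listed outcome nor one of the examples given for that route.

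TESAE incidence is part of the primary safety endpoint (Protocol 3.1.2). SAP 3.6.1 treats an AE as treatment-emergent by its onset relative to first dosing, summarizes TESAEs, and adds: "TESAEs will be summarized by SAE criteria as well". On overdose, SAP 3.6.3.1 says only this: "The incidence of TEAE associated with overdose will be summarized by MedDRA SOC and PT if applicable".

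**The concern.** Sections 8.9 and 8.1 apply different tests. One looks at what happened (an overdose), the other at what resulted from it. For most overdoses of clinical importance they may agree. They part for an overdose without a serious outcome that no one would judge an important medical event: 8.9 puts it on record as an SAE, and 8.1 does not make it serious.

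Neither document says which test governs the count. If the database flag follows 8.9, a non-serious occurrence enters the TESAE numerator of a primary safety endpoint. It also has no 8.1 criterion to be tabulated under, so the TESAE total and the table by criterion would not agree. If the question is left until such a case appears, it will be settled case by case, possibly after some sponsor staff have been unblinded for the Day 113 analysis.

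**Working it through.** The plan gives no figure to reproduce on this point. The check is a comparison of texts, followed by one piece of arithmetic.

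**1. Does 8.9 impose a seriousness condition?** No. It applies to suspected as well as confirmed overdoses and to any drug. No outcome has to be present.

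**2. Could 8.1 cover the same cases anyway?** In part. The view of either the investigator or the sponsor is enough, and the important-medical-event route can bring in overdoses that did not cause death, threaten life or lead to hospital admission. That route requires a judgment on each case and is not automatic. The conflict is confined to overdoses that meet no 8.1 criterion after that judgment has been made.

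**3. Is there a comparable rule that avoids the gap?** Yes. Appendix 2 of the protocol directs that confirmed Hy's Law cases be reported as SAEs and names the criterion to enter when no other applies (medically important). Section 8.9 has no equivalent sentence.

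**4. Can such a record reach the TESAE count?** It can, if it is held as an AE with an SAE flag and its onset is at or after first dosing. SAP 3.6.1 has no exception for records that are SAEs only because of 8.9. SAP 3.6.3.1 adds a table but removes nothing from the TESAE count.

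**5. Can such an overdose occur?** Study infusions are prepared by pharmacy staff and given by site staff (Protocol 7.2.3 and 7.3), which limits the opportunity there. But 8.9 is not limited to study drug. Inclusion criterion 6 requires every subject to be on methotrexate or, if it is not tolerated or is contraindicated, another conventional DMARD. Exclusion criterion 7 also permits stable low-dose oral corticosteroids. Follow-up runs to Day 309 for subjects without rescue. The documents give no overdose rate.

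**6. Size.**
- Inputs: 15 subjects per arm (Protocol 9.3; SAP 2.3); incidence counted as subjects with at least one event (SAP 3.6.1).
- Change in an arm's TESAE incidence = (subjects counted only because of 8.9) / 15.
- No such subject: 0/15 = 0.
- One: 1/15 = 6.7 percentage points.
- Two: 2/15 = 13.3 percentage points.
- An affected subject who already has another TESAE adds nothing, because subjects are counted once.

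For scale, Protocol 2.1.5.1 describes one SAE in the 57-subject phase 1b RA study, and 1/57 = 1.8%. The surrounding text is partly removed from the public version, so this is not a firm background rate.

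**The case against.** The strongest reply is that 8.9 describes a reporting channel and does not reclassify anything. It never says that an overdose is serious. Its 24-hour limit matches the SAE reporting time in Protocol 8.3, and its request for details reads like instructions for completing a form. On that reading 8.1 remains the only definition of seriousness and nothing is miscounted. This is a reasonable reading and may be what was intended. The text does not say so, however, and a site following the words could set the flag.

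A second reply is that an overdose with no untoward medical occurrence may not be an AE under 8.1 at all, and so could not be a TESAE. That stands as a further limit: whether such a record is an AE is itself unsettled, which is why the effect on the count is only possible.

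A third is that planned outputs would expose a stray case. TESAEs are tabulated by preferred term and by criterion, all events are listed, and overdose-associated TEAEs have their own table. This also stands. A careful reader could trace one record, which limits the harm but does not correct the headline percentage.

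Finally, 1/15 is the weight of any single event in an arm of this size and is not peculiar to overdose. That is correct. It shows scale and is not evidence that the problem will arise.

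**Conclusion.** The inconsistency is real but narrow. It affects only an overdose that meets no 8.1 criterion even on medical judgment, is held as an AE, and starts at or after first dosing. Each subject counted only for that reason moves an arm's TESAE incidence by 6.7 percentage points; if there is none, nothing changes. Safety is summarized descriptively (Protocol 9.5.3), so no test, error rate or power is involved.

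Three stronger conclusions are tempting, and the documents do not support them:
- A reader might infer that 8.9 contradicts 8.1 for every overdose, or for every one without symptoms. The important-medical-event route prevents that.
- A reader might infer that the primary safety comparison is biased. The documents give no overdose rate, and background treatment is required in all arms of a blinded study. What could follow is a stray count in any arm, placebo included.
- A reader might infer that SAP 3.6.3.1 already displays all overdoses. It covers only TEAEs associated with overdose, so an overdose without an AE would not appear there.

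This is a desirable clarification of low weight.

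**What to change.** Reconcile Protocol 8.9 with 8.1. Every overdose should still be communicated within 24 hours on the SAE form, while the seriousness flag follows 8.1, including the important-medical-event route. In SAP 3.6.1, state that TESAE counts use events meeting an 8.1 criterion, so that the total and the table by criterion agree. Extend SAP 3.6.3.1 to list all reported overdoses, with or without an associated AE, so that nothing is lost from view when the flag is not set.

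These changes concern classification and counting only. Rapid reporting is unaffected. The cost is one sentence in the protocol, two in the SAP, and a small amount of extra listing work. They are best made before any unblinding for the Day 113 analysis.
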